#### 6.0 Sources of Research Material

Data for this study will be gathered by caregiver report via the Food Neophobia Scale for Children (FNSC) questionnaire consisting of 10 questions and parent interview to gather information about the age and weight of the child (Pliner, 1994). Participants will complete the State-Trait Anxiety Inventory for Children (STAIC) S-Anxiety scale consisting of 20 questions (Spielberger, 1973). The guardians will also complete a food log. All data collected from the assessments will be used for research purposes. No data from records will be reviewed for this study. In addition, any protocol deviations or unanticipated problems will be monitored.

#### **6.0 Study Product Description**

A weighted blanket 10% or less of the participant's body weight will be used under parent or therapist supervision as a calming strategy prior to introduction to new food paired with a preferred stationary task such as watching a video or reading a book.

Weighted blankets are commercially available for children in weights of ten pounds, seven pounds, five pounds, and three pounds through the company yescool (yescool, n.d.). The blankets are made from glass beads and breathable polyester microfiber fabric according to the Amazon website. The glass beads are enclosed in five inch by 5 inch square compartments and stitched by high-density 15000 stitches to secure the glass beads within the blanket. Each participant will receive a weighted blanket that is approximately 10% of their body weight but does not exceed 10% of their body weight. For example, if a child weighs 55 pounds, they will receive a five-pound weighted blanket.

#### 7.0 Potential Risks

Risks for this program are limited, but some potential risks are possible.

- Loss of confidentiality.
- Risk of mild to moderate discomfort due to having to reflect upon things that may make them feel uncomfortable such as anxiety level and food
  - Risk of discomfort using the weighted blanket

#### 8.0 Subject Safety

This study controls for risk as all use of weighted blanket will be under adult supervision and not during sleep. In addition, the participant can refuse the use of the weighted blanket at any

time during the study limiting any psychological risk or adverse events. Any adverse events will be reported immediately.

Prior to the start of the study, researcher will discuss best practices for weighted blanket use and guardians will be provided with a handout detailing the protocol and safety guidelines. The guardian will have the blanket in their possession and will only offer the blanket during times detailed in the protocol. All subjects will be given the opportunity to exit the program and withdraw consent at any time if they determine that they are no longer able to participate. The researcher will be available via HIPAA compliant email throughout the study to answer any questions that may arise and offer support. In person meetings will also be available upon request. All data collected throughout the program will be maintained on password protected emails and computers to reduce the risk for breach of privacy.

[name] will provide supervision as the faculty sponsor through a weekly check-in via email, phone or zoom meeting with the principal investigator. The principal investigator will notify the faculty sponsor immediately via email with any questions or concerns. The principal investigator will include the faculty sponsor on any emails with the participants to ensure appropriate monitoring. All information pertaining to this study will be available to [name].

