### 4.0 Enrollment/Consenting Process

Children receiving occupational therapy services at Capital Area Speech and

Occupational Therapy to address feeding who have anxiety related to food will be offered enrollment via flyers and word of mouth. The first level of recruitment will include potential participants that have a patient relationship with the principal investigator or are receiving occupational therapy services from another occupational therapist at Capital Area Speech and Occupational Therapy. If 12 participants meeting the inclusion criteria cannot be recruited from Capital Area Speech and Occupational Therapy, the second level of recruitment will occur including other clinics in the Austin, Texas area who have given permission for flyers to be left in their waiting rooms. During the second level of recruitment, potential participants will contact the principal investigator for additional information regarding the study. A flyer will be available to potential participants with information about the study and principal investigator's contact information so that caregivers can ask questions. Potential study participants will only be provided additional information upon request regarding the study.

Recruitment will take place for 2 months and is anticipated to start April 2024 following IRB approval with researchers determining eligibility for the study based on inclusion and exclusion criteria. Participants and at least one guardian of each participant will be required to sign a consent form to affirm that they understand the purpose of this study, risks, and

requirements. To respect potential participant privacy, no information will be collected for research purposes prior to consent form completion. Also, no information of participants who withdraw from this study will be used. To consent to this study, potential participants will be provided with a consent form to review via email prior to signing it. Potential participants will be given an opportunity to speak with the investigator prior to signing the consent form.

No randomization will take place. There will be a control period consisting of usual care occupational therapy lasting 1 month prior to the treatment period lasting 1 month.

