#### 5.0 Study Procedures

- 1. Recruitment
- 2. Consent
- 3. Enrollment of participants based on inclusion and exclusion criteria.
- 4. Guardians of enrolled participants will complete the baseline outcome measure

  Food Neophobia Scale for Children (FNSC) questionnaire consisting of 10 questions

  (Pliner, 1994). Guardians of participants will also complete an initial food list on the
  initial food log form including all foods that the participant currently tolerates. Included
  on the initial food log form will be a place for the caregiver to record the age and weight
  of the child. The weight of the child will be used to calculate the appropriate weight of
  the weighted blanket. The weighted blanket will not exceed 10% of the child's body
  weight. Weighted blankets are commercially available through the company yescool for
  children in weights of ten pounds, seven pounds, five pounds, and three pounds. Each
  participant will receive a weighted blanket that is approximately 10% of their body

weight but does not exceed 10% of their body weight. For example, if a child weighs 55 pounds, they will receive a five-pound weighted blanket. The initial food log form including the initial food list and weight of the child will be scanned and returned to the caregiver prior to the control period. The FNSC will be collected.

- 5. Participants will receive occupational therapy services treatment as usual without use of a weighted blanket for 1 month. During this period, participants will complete the S-Anxiety scale of the State-Trait Anxiety Inventory for Children (STAIC) three times per week upon sitting at the table prior to a meal (Spielberger, 1973). The S-Anxiety scale questionnaire will take about 8-12 minutes for a child to complete the first time and 5-8 minutes for repeated administrations. All forms and scales necessary for the control period will be provided to the caregivers prior to the control period of the study.
- 6. After the 1-month control period, caregivers will complete the FNSC and complete the second food list adding any new foods to the initial food log (Pliner, 1994). The principal investigator will collect the FNSC and the initial food log form at this time.

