- 7. Following the 1-month control period, participants and their guardians will receive a weighted blanket with verbal and written instructions for use and safety. The participants will continue usual care occupational therapy treatment during the treatment period. The caregivers will be provided with copies of the S-Anxiety scale of the STAIC, new food log, and a copy of the initial food log for reference (Spielberger, 1973). Participants will be instructed to use the weighted blanket for at least 5 minutes and no more than 15 minutes while participating in a quiet enjoyable activity prior to a meal with guardian supervision. Guardians will be responsible to keep the weighted blanket when not in use. Due to busy family schedules, it may not be possible to use

the blanket daily, therefore, the family will be asked to offer use of the blanket a minimum of 3 meals a week. On the days that the weighted blanket was used, the participant will complete the S-Anxiety scale of the STAIC at the table where they will consume the meal, following using the blanket and before eating the food (Spielberger, 1973). The guardians will be asked to record any new foods tried during the meal on the new food log along with the date each time the participant uses the weighted blanket.

- Upon completion of the 1-month treatment period, the guardians will complete the FNSC (Pliner, 1994). The principal investigator will collect the FNSC, new food log, and S-Anxiety scale of the STAIC at this time either through HIPAA protected email or in-person (Spielberger, 1973).
- 10. Once the study is completed the guardians will be gifted the weighted blanket to use as they deem appropriate

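### Section 8.0 times the weighted-blanket discussion and handout before the study, section 5.0 times the instructions after the control month; the early timing can dilute the only comparator and the two must be reconciled

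*Combined protocol and SAP*

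**What the plan says.** The design is a single group in fixed order, without randomization. Section 4.0 states: "There will be a control period consisting of usual care occupational therapy lasting 1 month prior to the treatment period lasting 1 month".

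Three places bear on when families learn how the blanket is used:

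- **Section 8.0 (Subject Safety):** "Prior to the start of the study, researcher will discuss best practices for weighted blanket use and guardians will be provided with a handout". The sentence goes on to say that the handout covers the protocol and the safety guidelines.
- **Section 5.0, step 5 (control month):** "Participants will receive occupational therapy services treatment as usual without use of a weighted blanket for 1 month". On what is supplied beforehand, the same step says: "All forms and scales necessary for the control period will be provided to the caregivers prior to the control period of the study". It mentions no blanket material.
- **Section 5.0, step 7 (start of treatment):** "Following the 1-month control period, participants and their guardians will receive a weighted blanket with verbal and written instructions for use and safety".

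Section 8.0 also limits use: "The guardian will have the blanket in their possession and will only offer the blanket during times detailed in the protocol". Section 12.0 compares the treatment and control periods by paired t-test on the S-Anxiety mean, the FNSC raw score and the number of new foods tried.

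**The concern.** Each child serves as his or her own control, and there is no parallel group. The control month is therefore the only thing against which the treatment month can be judged.

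Part of the intervention needs no study blanket. Step 7 has the child use it "while participating in a quiet enjoyable activity prior to a meal with guardian supervision", and a family told of this routine can begin the quiet activity at once. The blanket is not exclusive to the study either: "Weighted blankets are commercially available for children in weights of ten pounds, seven pounds, five pounds, and three pounds", according to section 6.0 (Study Product Description).

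If families are coached a month early and some act on it, part of any benefit falls in the control month. The treatment-minus-control difference then shrinks on all three outcomes. With seven to twelve children, a few families are enough to matter. No form in the plan asks about such use.

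**Working it through.** **1. The passages side by side.** The plan states no figure on this point, so there is none to reproduce. The first check is textual.

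| Item | Section 8.0 | Section 5.0 |
|---|---|---|
| Spoken guidance on blanket use | Before the study starts | Step 7: with the blanket, after the control month |
| Written guidance | Handout, before the study starts | Step 7: with the blanket, after the control month |
| Supplied before the control month | Discussion and handout | Step 5: forms and scales for that month |
| Study blanket itself | Held by the guardian, offered only at protocol times | Step 7: after the control month |

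Could the start of the study mean the start of treatment? Not naturally. Baseline measures, the control month and the end-of-control collection are numbered study procedures (steps 4 to 6) and all come before treatment. The timings of the guidance therefore differ by at least the control month. The timing of the blanket itself is not in conflict.

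**2. Which routes remain open in the control month.**

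- Early use of the study blanket: closed, because it has not been delivered.
- A family-owned or purchased blanket: contrary to step 5, but possible.
- The quiet pre-meal activity without a blanket: not mentioned in step 5 and not restricted anywhere.

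**3. Direction and illustrative scale.** Let c be the share of families who follow the routine throughout the control month, q the share of the full effect they obtain from it, and D the true mean effect. The control month already contains c × q × D, so

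observed difference = D − c × q × D = (1 − c × q) × D.

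Neither c nor q is given in the documents; both are assumptions. Section 2.0 (Proposed Pilot Study) gives the sample sizes: a minimum of 7, with permission sought for 12.

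| Families adopting early | c | Loss at q = 1 | Loss at q = 0.5 |
|---|---|---|---|
| 1 of 7 | 0.143 | 14% | 7% |
| 3 of 7 | 0.429 | 43% | 21% |
| 1 of 12 | 0.083 | 8% | 4% |
| 3 of 12 | 0.250 | 25% | 12.5% |

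For a family doing only the quiet activity, q = 1 would mean that the blanket adds nothing, so that column is an upper limit.

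**4. What a given loss would do to a paired t-test.** The plan gives no alpha, power, effect size or standard deviation. Assume a two-sided alpha of 0.05 and a true standardized paired effect d that gives 80% power without dilution: d = 1.273 at n = 7 and d = 0.889 at n = 12. With loss L = c × q and an unchanged standard deviation of differences, the effect becomes (1 − L) × d, and power follows from the noncentral t distribution with n − 1 degrees of freedom and noncentrality (1 − L) × d × √n.

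| Loss L | Effect, n = 7 | Power, n = 7 | Effect, n = 12 | Power, n = 12 |
|---|---|---|---|---|
| 0 | 1.273 | 0.800 | 0.889 | 0.800 |
| 10% | 1.145 | 0.715 | 0.800 | 0.713 |
| 25% | 0.954 | 0.562 | 0.666 | 0.558 |
| 50% | 0.636 | 0.295 | 0.444 | 0.290 |

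Both tables show direction and sensitivity. They do not forecast what will happen in this study.

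**The case against.** **The two sections may describe two contacts.** Section 8.0 could mean an early safety briefing and step 7 the working instructions; nothing says the materials are the same. That is possible, but section 8.0 would still put guidance on blanket use and a protocol handout ahead of the control month, and that early contact is the exposure.

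**The plan already limits contamination.** This stands. The study blanket is not delivered early, step 5 makes the month blanket-free, and a handout that sets out the protocol might well tell families to wait. A reader might infer that the control month will be contaminated. The documents support only that it can be.

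**Families know about the blanket anyway.** This stands too. Under section 4.0 they sign that they understand the purpose and requirements before the control month, and under section 3.0 refusing the blanket is an exclusion, so it has to be raised at screening. Retiming the handout removes advance coaching in technique, not expectancy.

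**Two further inferences fail.** A reader might conclude that early use could never be found out. But section 6.0 (Sources of Research Material) says protocol deviations will be monitored, and guardians can be asked at the step 6 collection; what is missing is a specific question. A reader might also see a month's gap between safety advice and first use. Step 7 gives safety instructions with the blanket, so there is no such gap when it is followed.

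**The percentages have no source.** Correct. The 43% figure needs the minimum sample, three families adopting throughout, and the full effect in each.

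**Conclusion.** The inconsistency is certain from the text, and the passages must be reconciled. Its consequence is a possibility: advance guidance can lead some families to adopt the pre-meal routine or use their own blanket in the only comparator month. If the routine works, the treatment-control difference is then biased toward zero.

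The documents cannot quantify that bias. The illustrative losses run from 4% (one of twelve families, half the effect) to 43% (three of seven, the full effect), and rest wholly on assumed values of c and q. The remaining route is narrow.

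This is an inexpensive improvement worth making before enrollment. It is not a flaw that invalidates the comparison.

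**What to change.** 1. In section 8.0, time the blanket-use discussion and the handout to the blanket handover, once the control-month forms are completed, so that it matches step 7. Before the control month, give families only that month's forms and the instructions for them, apart from what consent and eligibility screening require.
2. At the step 6 collection, add one question to the guardian: was any weighted blanket, or any calming routine before meals, used during the control month, and about how often? Report the answers beside the paired comparisons.

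The cost is one reworded sentence and one added question, with no extra visit. The trade-off is the loss of an earlier briefing; instruction on use and safety is still given when the blanket is handed over. The change does not remove expectancy, which arises from consent.

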#### 9.0 Data Monitoring and Participant Confidentiality

Data from questionnaires and food logs will be kept on password protected computers to ensure protection of participants confidentiality. No discussion of participants' information will be discussed in public settings and all data analysis will be performed in private settings.

#### **10.0 Potential Benefits**

By participating in this program, participants are expected to gain a better understanding of their own anxiety related to food and if a weighted blanket is beneficial to help them feel calmer and more regulated. The program aims to improve the everyday living experience of participants as it relates to mealtime. Participants will be provided with a weighted blanket for continued use as needed.

# 11.0 Study Withdrawal/Discontinuation

Possible reasons for withdrawal from this study:

- 1. Time commitment
- 2. Participant no longer wants to use the weighted blanket
- 3. Use of weighted blanket becomes contraindicated
- 4. Discontinuation from occupational therapy services

Handling withdrawals:

Withdrawal from the study will be accepted and an interview regarding reasons for withdrawal will be completed.

Termination of this study will occur if there are no participants willing and able to participate.

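### Section 11.0 collects reasons for withdrawal but Section 4.0 bars using any information from children who withdraw, so stopping because of the blanket cannot appear in the results

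*Combined protocol and SAP*

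**What the plan says.** - **Section 7.0 (Potential Risks)** names "Risk of discomfort using the weighted blanket" among the risks.
- **Section 11.0 (Study Withdrawal/Discontinuation)** lists four possible reasons for leaving. Two concern the blanket: "Participant no longer wants to use the weighted blanket" and "Use of weighted blanket becomes contraindicated". The other two are the time commitment and the end of occupational therapy. The same section then says: "Withdrawal from the study will be accepted and an interview regarding reasons for withdrawal will be completed".
- **Section 4.0 (Enrollment/Consenting Process)** says that "no information of participants who withdraw from this study will be used". It makes no exception for safety information or for the reason given on leaving.
- **Section 12.0 (Biostatics and Subsidies)** plans comparisons of the S-Anxiety score, the food neophobia score and the number of foods tried. It plans no summary of withdrawals, their reasons or adverse events.
- **Section 8.0 (Subject Safety)** says that "the participant can refuse the use of the weighted blanket" at any time, without equating refusal with withdrawal. It adds: "Any adverse events will be reported immediately". The section headed Sources of Research Material says that deviations and unanticipated problems will be monitored.

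**The concern.** The plan asks for a piece of information in one section and forbids its use in another. The information concerns a risk that the plan itself names, and the loss is selective: a child who leaves because of the blanket drops out of the results together with the reason.

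Section 1.0 reports finding no studies of weighted blankets in children with anxiety-related food avoidance. Whether children keep using the blanket is therefore basic information for a pilot meant to inform therapists. The issue is how stopping and harm are reported. It is separate from the effect of dropout on the paired efficacy comparisons.

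**Working it through.** There is no stated figure to reproduce. The documents give no withdrawal rate, tolerability rate or adverse event rate. The check is a comparison of the text, followed by an illustration.

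**Step 1: the two rules side by side.** Section 11.0 requires that "an interview regarding reasons for withdrawal will be completed". Section 4.0 says no information from those who withdraw is used. Everyone who has that interview has withdrawn, so the bar covers every interview. Section 12.0 does not restore the information, because it has no table for it.

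**Step 2: do other instruments fill the gap?** The scheduled instruments are the food neophobia questionnaire, the S-Anxiety scale and the food logs. None is described as asking about discomfort or refusal. In the treatment month the S-Anxiety scale is tied to days of blanket use (Section 5.0, item 7), so a day of refusal produces no form. Adverse event reporting and monitoring of unanticipated problems depend on an event being recognised. A child who simply stops wanting the blanket may trigger neither. Neither route has a place in the planned analysis.

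**Step 3: illustration.** Inputs:
- 12 children, the number for which the Proposed Pilot Study part of Section 2.0 seeks permission.
- Assumed: all 12 receive a blanket, w of them withdraw because of it, and none withdraws for another reason.

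The proportion among all treated children is w/12. Among those who stayed, the count of blanket-related withdrawals is 0 out of 12 − w, by construction. Exact (Clopper-Pearson) 95% limits for x of n are the 2.5% point of Beta(x, n − x + 1) and the 97.5% point of Beta(x + 1, n − x). With x = 0 the lower limit is 0 and the upper limit is 1 − 0.025^(1/n).

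| w (assumed) | All treated, w/12 (95% CI) | Stayed, 0/(12 − w) (95% CI) |
|---|---|---|
| 1 | 8.3% (0.2 to 38.5%) | 0/11 (0 to 28.5%) |
| 2 | 16.7% (2.1 to 48.4%) | 0/10 (0 to 30.8%) |
| 3 | 25.0% (5.5 to 57.2%) | 0/9 (0 to 33.6%) |
| 4 | 33.3% (9.9 to 65.1%) | 0/8 (0 to 36.9%) |
| 5 | 41.7% (15.2 to 72.3%) | 0/7 (0 to 41.0%) |

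For w = 3: 3/12 = 25%, while the usable data show 0/9, with upper limit 1 − 0.025^(1/9) = 33.6%. The zero in the right-hand column is fixed by the rule and does not depend on what happens to the children.

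**Step 4: how likely is at least one such withdrawal?** With an assumed chance q per treated child, it is 1 − (1 − q)^12. This gives 1 − 0.95^12 = 46% for q = 5%, 1 − 0.90^12 = 72% for q = 10%, and 1 − 0.80^12 = 93% for q = 20%. The values of q are assumptions.

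**The case against.** The strongest reply is that the plan makes no claim about tolerability. Its aims are calming and novel food consumption, and safety is handled outside the statistics: adverse events are reported immediately with no exception for withdrawn children, unanticipated problems are monitored, and the faculty sponsor has weekly check-ins. The Section 4.0 sentence comes just after one about privacy and information collected for research. It can be read as a rule about research data, which leaves the interview free for oversight. Much of this stands, and it rules out several stronger readings:

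- **That the study will issue a misleading tolerability statement.** A reader might infer this, but no such statement is planned. The point is conditional: if one were drawn from the usable data, it would be biased.
- **That all tolerability information would come from children who tolerated the blanket.** A child may refuse it or find it uncomfortable and stay in the study, and event-driven reports may record that.
- **That the bar removes exactly the intolerant children.** It removes everyone who withdraws, including those who leave for lack of time or because therapy ended. No longer wanting the blanket also need not mean discomfort.
- **That adverse events in withdrawn children would go unreported.** Section 8.0 requires reporting without exception. Whether the Section 4.0 bar keeps those events out of the results is unclear.
- **That the plan allows up to 5 blanket-related withdrawals, giving 0/7 with an interval that excludes the truth.** Seven is a recruitment minimum, not a required number of completers. The upper limit of 41.0% falls below 41.7% only in that extreme row. At w = 3 or 4 the interval for those who stayed includes the all-treated proportion. The blanket is also issued only after the control month, so fewer than 12 may ever receive it.

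The privacy reading does not remove the conflict. The sentence covers all information, states no exception, and nothing in Section 11.0 says what the interview is for.

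**Conclusion.** The conflict between Sections 4.0 and 11.0 is real, and Section 12.0 does not resolve it. Followed as written, the number of children who stopped because of the blanket cannot appear in the results, and any remark on acceptability or discomfort based on the usable data would be biased towards children who stayed. The other safety routes limit the gap without closing it.

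The size cannot be estimated from the documents. The figures above are illustrations that assume 12 treated children and an invented number or rate of blanket-related withdrawals. The point concerns reporting. It changes no efficacy test, sample size or error rate, and it takes no position on when blanket use should stop.

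**What to change.** 1. **Section 4.0:** limit the bar so that it does not cover adverse events or the reason for withdrawal given in the Section 11.0 interview. The consent form was not available for this check. If it does not already allow this use, add matching wording approved by the IRB.
2. **Section 12.0:** add a descriptive summary giving the number enrolled, the number who received a blanket, the number who withdrew in the control month and in the treatment month with reasons (including reason not given), and any adverse events. Use all children who received a blanket as the denominator for blanket-related events.

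The cost is a sentence in Section 4.0, possibly one in the consent form, and one table. The interview is already planned, so no visit or staff is added. The downside is that limited safety information from families who leave is kept. Precision will be low whatever is done: even 0/12 has an exact 95% upper limit of 1 − 0.025^(1/12) = 26.5%. The summary should therefore be read as description only.
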